5.4 Inclusion/Exclusion Criteria

Patients:

Inclusion Criteria

- Receives primary +/- nephrology care from VAPS as defined as having at least 1 outpatient primary or nephrology visit in the prior year
- Adults aged ≥ 18 years
- Advanced CKD as defined as having ≥ 2 outpatient measures of an eGFR ≤ 20 ml/min/1.73m² separated ≥ 90 days
- Unsure or do not wish to undergo maintenance dialysis
- Agreement by their VA primary +/- nephrology care provider that patients can participate in the study

Exclusion Criteria

- Unable to complete "teach-back" method of informed consent
- Currently receiving maintenance dialysis
- Currently enrolled in HBPC Program

Caregivers:

Inclusion Criteria

- Adults aged ≥ 18 years
- Nominated by enrolled patient as a caregiver whom patient agrees to participate in the study

Exclusion Criteria

- Unable to complete “teach-back” method of informed consent

A Veteran who does not identify a caregiver or whose nominated caregiver does not wish to participate in the study, the Veteran is still eligible to participate in the study. If a Veteran withdraws from the study, their caregivers’ participation in the study is also terminated at that time.

Clinicians:

Inclusion Criteria

- Employed at VAPS
- Identified by enrolled Veterans as important to their CKD and nominated by the Veteran to be interviewed for the study

Exclusion Criteria

- None

For a Veteran who does not identify a clinician or whose nominated clinician does not wish to participate in an interview, the Veteran will still be eligible to participate in the study. If a Veteran withdraws from the study, their clinicians will no longer be eligible to participate in interviews.

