5.5 Interventions

For each consecutively enrolled Veteran, the investigators will randomly assign the Veteran and their caregiver to either usual care (i.e., control arm) or to the Kidney Care at Home Program (i.e., intervention arm). Randomization to each study arm will be computer generated with a 1:1 allocation.

Usual Care: Veterans with advanced CKD are typically cared for by a VAPS primary care provider. Additionally, they might receive specialty nephrology care at the VA. Enrolled Veterans who are assigned to usual care will continue to receive the care they had been receiving for their CKD by their primary care +/- nephrology provider.

Intervention: Enrolled Veterans and their caregivers who are assigned to the intervention will be enrolled in the Kidney Care at Home Program. The Program will be delivered through the existing HBPC infrastructure at VAPS. The HBPC Program at VAPS is comprised of 8 HBPC teams, and each team is comprised on a lead physician or nurse practitioner, nurse, pharmacist, nutritionist, social worker, psychologist, therapist, and chaplain. Veterans will be assigned to the HBPC team serving their residential area. As is the standard of care for HBPC services, each member of their HBPC team that will perform an initial assessment of each Veteran within 3-months of randomization. This includes review of each Veteran’s medical history and assessment of unmet medical and psychosocial needs. Additionally, the HBPC team will perform a focused CKD symptom assessment. On a monthly basis, the entire HBPC team will conduct MDC meetings to review each Veteran’s active medical issues, recent hospitalizations, and emergency room visits, psychosocial needs, and medical plan.

At a minimum, subsequent clinical encounters and assessments for each Veteran will be scheduled no less than on a quarterly basis and more often as needed based on the HBPC team’s clinical judgment. The HBPC team will also treat identified problems and make appropriate referrals according to their discretion and clinical judgment. The HBPC Team will

also have the freedom to change the frequency of their visits and the different team members involved in a patient's care according to their clinical judgement.

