All clinical encounters, phone contact, and correspondence between a Veteran and any HBPC team member as part of the Program will be documented in the VA electronic medical record. Notes from monthly MDC meetings will also be documented in the medical record. The investigators will also be available between MDC meetings for urgent patient care-related questions.

Because the Program will provide both primary and nephrology care, enrolled Veterans will transfer their primary +/- nephrology care to the CC Program. The CC Program will also continue to follow Veterans through hospital and nursing home admissions and to care for Veterans if they should change their minds and start dialysis and/or return to CC after a trial of dialysis so as to support care flexibility and continuity. Should Veterans withdraw from the study, the Program will assist the Veteran with returning to their original primary care +/- nephrologist. After Veterans complete the study, they will be given the option to continue with the Program for ongoing primary and CC until they no longer desire it or to return to their original primary care +/- nephrologist.

The investigators will oversee implementation of the Program. In addition to the usual primary care provided by HBPC services, the Program will provide CC to enrolled subjects. The Program will incorporate the following CC care: patient-centered, whole-person and team-based care, shared decision-making, active symptom management, advance care planning and end-of-life care.¹⁵ Specific care items reflecting these CC elements will draw from the clinical expertise of the investigative team, CC educational materials prepared by the investigative team, international consensus statements on CC best practices,²¹ publicly available provider and patient resources on CC, and existing patient resources on related topics of kidney disease, self-care, and home and community-based resources that support Veterans' independence at home from the VA Kidney, Whole Health, and GEC Programs.

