5.6 Study Evaluations

The investigators will use a combination of surveys, interviews, field observations, and medical record review to compare usual care and the Kidney Care at Home Program. Subjects will be followed through death, study withdrawal, or 1-year follow-up, whichever comes first. Subjects will be asked to complete the following procedures at enrollment and every 3 months (+/- 1 month) following randomization. Veterans and caregivers will receive a \$40 incentive for each study visit that they complete (total of \$200). Clinicians will not be provided compensation for their participation.

Surveys:

Demographic survey: At enrollment, Veterans and caregivers will be asked to complete a brief survey to collect information about their age, race, ethnicity gender, educational background, marital status, employment status, and annual household income. Each caregiver will also be asked their relationship to the Veteran, hours spent caregiving for the Veteran per week, and types of caregiving provided to the Veteran. For clinicians who participate in interviews, The investigators will ask their age, race, gender, professional role, year in clinical practice, and medical specialty.

Health Outcomes Prioritization Scale: At each study visit, The investigators will ask Veterans about their preference for care to be directed at maintaining independence, maximizing longevity, reducing or eliminating pain, and reducing or eliminating dizziness, fatigue, and shortness of breath using the Health Outcomes Prioritization Scale.²² Veterans will also be asked whether they view the care they receive for their kidney disease as focused more on independence, longevity, pain relief, or relief of other symptoms. The language using in the Scale will be slightly

adapted to support a 7th grade literacy level. The investigators will slightly adapt the Scale for caregivers to inquire their perception of patients' healthcare priorities and the kind of care that patients receive.

Zarit Burden Interview: With caregivers at each study visit, the investigators will administer a 12-item survey that asks caregivers to rate the frequency with which they experience different forms of caregiver strain (nearly always).²³

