Healthcare utilization: The investigators will record all hospital, nursing facility, emergency room use, and palliative care consultations documented in the medical record during follow-up. The investigators will also record any hospice, social work, nutrition, pharmacy, therapist, mental health, and chaplaincy referrals and visits during follow-up.

Dialysis status for advanced CKD: The investigators will record whether Veterans changed their mind about CC and received dialysis during follow-up.

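### The exploratory utilisation summary does not separate the Program's own team visits in six disciplines from other healthcare use, and it names no follow-up time to set beside the counts

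*Combined protocol and SAP*

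**What the plan says.** Section 5.6 (Healthcare utilization) records hospital, nursing-facility and emergency use and palliative consultations, and then adds: "The investigators will also record any hospice, social work, nutrition, pharmacy, therapist, mental health, and chaplaincy referrals and visits during follow-up". It gives no rule on whether contacts made by the Program's own team are included.

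Section 5.5 describes each HBPC team as a lead physician or nurse practitioner plus "nurse, pharmacist, nutritionist, social worker, psychologist, therapist, and chaplain". For intervention Veterans, "each member of their HBPC team that will perform an initial assessment of each Veteran within 3-months of randomization". Later encounters are at least quarterly, and the team has "freedom to change the frequency of their visits and the different team members involved". The VA chart is named as the place where Program contacts are written up: "All clinical encounters, phone contact, and correspondence between a Veteran and any HBPC team member as part of the Program will be documented". Section 5.4 excludes Veterans who are "Currently enrolled in HBPC Program".

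Section 5.6 opens by saying that surveys, interviews and observations will be used together with "medical record review to compare usual care and the Kidney Care at Home Program". It also fixes the observation period: "Subjects will be followed through death, study withdrawal, or 1-year follow-up, whichever comes first". Section 5.8 keeps de-identified data collected before a withdrawal.

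Section 5.7 plans to describe utilisation and dialysis treatment, as exploratory analyses, with proportions and means as suits the measure. Attrition rates and reasons for withdrawal are planned too, but under feasibility and acceptability, without a link to utilisation.

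**The concern.** A utilisation table by arm is normally read as showing what care patients used under each approach. In six of the recorded categories, part of the intervention arm's count is the intervention itself, placed there by the protocol. Without a split, a reader cannot tell whether a higher social work or chaplaincy figure means that the Program was delivered or that Veterans used more of these services elsewhere. Both are worth knowing, but they answer different questions: the first belongs to the Implementation domain of RE-AIM (section 5.1), the second to the exploratory outcomes.

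The secondary issue is that Veterans are observed for different lengths of time. A mean count, or the proportion with any use, falls when follow-up is shorter. If exits differ between the arms and follow-up time is not shown, shorter observation can look like lower use.

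**Working it through.** The documents give no visit rates, exit rates or sample-size calculation, so there is no planned figure to reproduce.

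**1. Matching the categories (sections 5.6 and 5.5)**

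| Recorded as utilisation | Program team role |
|---|---|
| Social work | Social worker |
| Nutrition | Nutritionist |
| Pharmacy | Pharmacist |
| Therapist | Therapist |
| Mental health | Psychologist (an interpretation) |
| Chaplaincy | Chaplain |
| Hospice | None |

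Six of seven match. Because current HBPC enrollees are excluded, at entry these team visits arise only in the intervention arm.

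**2. Counting protocol-driven initial visits**

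Up to 30 Veterans (section 5.2) at 1:1 allocation (section 5.5) gives about 15 per arm.

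- Ceiling: 15 × 6 = 90 visits, and 15 of 15 with any visit in each discipline.
- Assumed 60% delivery, because the team may vary its members: 90 × 0.6 = 54 visits, and 15 × 0.6 = 9 of 15 per discipline.
- Early exit: under the heavier assumed exit in step 3 (H = 0.580 per year), the share still in the study at 3 months is e^(−0.580/4) = 0.865, about 13 of 15. If those who left had received no assessment, the count would be 13 × 6 = 78.

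Later quarterly encounters are left out because their discipline is not stated. Referrals are not counted either.

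Effect on the proportion with any visit: suppose non-Program use of a discipline is p in both arms, and a share d of intervention Veterans receives the Program assessment independently of other use. The arms then differ by d(1 − p) with no difference in other use. For assumed p of 20%, 40% and 60%, this is 80, 60 and 40 points at d = 1, and 48, 36 and 24 points at d = 0.6.

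**3. Follow-up time (every input assumed)**

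Take 2 admissions per person-year in both arms and constant exit hazards. One arm has 15% deaths and 10% withdrawals over the year; the other has 30% and 20%.

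- H = −ln(1 − death) − ln(1 − withdrawal) = 0.268 and 0.580.
- Mean follow-up = (1 − e^(−H))/H = 0.877 and 0.759 years. For 15 per arm this is 157.9 and 136.6 person-months.
- Mean admissions = 2 × follow-up = 1.75 and 1.52. The ratio is 0.87, or 1.16 with the arms swapped.
- Ever admitted = 2/(2 + H) × (1 − e^(−(2 + H))) = 79% and 72%.
- Milder case, 20%/10% against 25%/15%: follow-up is 0.852 and 0.805 years, ratio 0.94.
- Sampling noise: about 26.3 and 22.8 admissions give a 95% factor of exp(1.96 × √(1/26.3 + 1/22.8)) = 1.75 either way. This assumes Poisson counts; overdispersion would widen it.

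**4. Does a person-month rate repair this?**

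Only if use is unrelated to exit. Let admissions be m times as frequent in the last 3 months before death, with death hazards h = −ln(0.85) = 0.1625 and −ln(0.70) = 0.3567. The rate per person-month is (2/12) × [1 + (m − 1)(1 − e^(−0.25h))].

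- m = 3: rates 0.180 and 0.195, ratio 1.08; means 1.89 and 1.78, ratio 0.94.
- m = 2: rate ratio 1.04; mean ratio 0.90.

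At m = 3 the rate is slightly further from 1 than the mean, and in the opposite direction. At m = 2 the rate is closer.

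**The case against.** The strongest reply is that the plan draws no inference here. Section 5.7 only describes utilisation, as exploratory work; there is no test and no utilisation hypothesis, and section 3.0 hypothesises only feasibility and acceptability. Total contact, Program visits included, is a legitimate quantity, because more multidisciplinary contact is a real difference in care received. The contacts are charted, so the split could be made at reporting.

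Much of this stands, and it is why the point is minor. It does not remove the ambiguity: a pooled count cannot be taken apart by a reader. Section 5.6 asks for provider type and setting for text abstracted from progress notes, but the utilisation paragraph requires no Program flag, so recovering the split later could mean re-reading charts.

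On follow-up time, the reply is that the wording of section 5.7 leaves rates open, that attrition is already reported, and that the illustrated shifts of 6% to 13% are small against a noise factor of 1.75. That is fair. It leaves a case for showing follow-up time and exits, but not for presenting rates as a correction.

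A reader might infer three stronger things that the documents do not support:

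- That any-use in the six disciplines will be 100% in the intervention arm by design. Veterans may leave before the 3-month assessments are complete, and the team may change which members are involved, so 15 of 15 is only a ceiling.
- That the whole utilisation comparison is contaminated. Hospital, emergency, nursing-facility, palliative and hospice use lie outside the overlap.
- That a six-discipline table would show little beyond delivery. That depends on usual-care use and non-Program use, for which the documents give no figures.

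**Conclusion.** The concern holds in limited form. As written, the plan counts protocol-driven Program visits as utilisation in six categories and does not say that they will be shown apart. The overlap is up to 6 initial visits per intervention Veteran who stays long enough to receive them: at most 90 in about 15 Veterans, or 54 at an assumed 60% delivery. This rests on full recruitment, on reading the psychologist as mental health, and on counting initial assessments only.

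The missing follow-up time is a real but secondary underspecification. It touches all utilisation and dialysis summaries, but its size cannot be derived from the documents and is likely below sampling noise at about 15 per arm.

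The primary feasibility and acceptability aim is unaffected. Severity: minor; a cheap improvement.

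**What to change.** - **Section 5.6, Healthcare utilization:** flag each recorded visit in the six disciplines as Program or non-Program at the time of abstraction.
- **Section 5.7, Exploratory analyses:** tabulate Program contacts as intervention delivery, under RE-AIM Implementation, and describe non-Program use separately by arm.
- **Section 5.7, follow-up time:** for hospital, emergency, nursing-facility, palliative and hospice use, give total follow-up time, deaths and withdrawals by arm, and add events per person-month beside the planned means and proportions. State that rates do not fully correct for unequal exit when use rises before death.
- **Section 5.7, dialysis:** show dialysis starts together with deaths before dialysis, by arm.

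The cost is slightly more abstraction and tabulation. The sources are already in the plan: Program contacts are charted, and death or withdrawal already ends follow-up. The flag should be agreed before abstraction begins.

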5.7 Data Analysis

Feasibility and acceptability: As the primary aim, the investigators will perform an inductive thematic analysis²⁸ of all qualitative data collected through interview transcripts, observational field notes, and passages from reviewed documents to ascertain the feasibility and acceptability

of approaches to caring for Veterans who are do not wish to forgo dialysis with usual care vs. the Kidney Care at Home Program. The investigators will triangulate the qualitative research findings with quantitative measures collected that also reflect feasibility and acceptability of care approaches. The investigators will describe enrollment and attrition rates, the reasons for refusal and withdrawal of study, and care satisfaction scores using proportions and means where appropriate. HBPC providers will not actively be sought as the primary target for interviews or observed encounters. However, if they are identified as being important to a Veteran's CKD care, acceptability and feasibility from the perspective of HBPC clinicians may be ascertained. Participation of HBPC clinicians would be based upon identification by Veterans, rather than their role within HPBC.

Exploratory analyses: The investigators will describe healthcare utilization, caregiver burden, healthcare goals, perceived care, quality of life, and treatment with dialysis during follow-up using proportions and means where appropriate. Level of agreement in perception of healthcare goals and goal concordant care between Veterans and caregivers will be reported using the kappa statistic.

5.8 Withdrawal of Subjects

Subjects may withdraw from the study at any time. The investigators will inform subjects that any de-identified data collected prior to their withdrawal will be included in analyses. For Veterans who withdraw from the study, The investigators will facilitate their transfer back to the VA primary care +/- nephrology provider caring for the Veteran prior to the study. The lead physician or nurse practitioner of the HBPC team will contact the Veteran's prior primary care +/- nephrology provider to review the Veteran's clinical course during their participation in the study, and discuss any active clinical issues that requires close follow-up.

5.9 Potential Risks and Benefits

Anticipated Risk:

Discontinuity in care: Veterans randomized to the Kidney Care at Home Program will transfer their primary +/- nephrology care from their existing primary care +/- nephrology provider to the Program. It can take time for Veterans to become comfortable interacting with a new clinical team and for the clinical team to get to know Veterans and familiarize themselves with Veterans' clinical history. This can lead to delays in addressing health problems. To minimize this risk, the investigators will arrange that each patient have their first visit with the Program clinicians within 3-months of enrollment in the Program. The lead physician or nurse practitioner of each Veteran's HBPC team will also contact each Veterans' primary care +/- nephrology provider to inform them of the date of their first visit with the Program clinicians and to obtain any pertinent history or active medical issues that require close monitoring at the outset of patients' participation in the Program. These measures will help to ensure continuity in care for patients.

Emotional or psychological unease: Subjects might feel uncomfortable during interviews discussing their care experience or when observed during encounters. To minimize this risk, throughout the course of the study and with each study visit, The investigators will verbally confirm their consent before undertaking each interview and survey and being observed. The investigators will assure subjects that they can choose not to answer any questions or complete any study procedure that they are not comfortable with. The investigators will also assure subjects that they can choose not to be observed.

Potential Benefits: The Kidney Care at Home Program will be the first evidence-based CC program for Veterans with advanced CKD in the VA, if not the nation. Veterans and caregivers randomized to receive care through the Program may derive benefit from receipt of CC.

Clinicians involved will receive formal training in CC, which may enhance clinical services for Veterans beyond those who participate in this study. The findings of this study will also inform how usual care services could also be improved for Veterans who do not wish to undergo dialysis and the caregivers and clinicians who support them. Completion of surveys and participation in interviews may encourage Veterans, caregivers, and clinicians to reflect on the meaning of their own care experiences which may be beneficial to them in and of itself.

6.0 Reporting

The investigators do not anticipate any adverse events that might occur. However, any and all unanticipated problems, serious adverse events and protocol deviations will be recorded and reported immediately to the study Principal Investigator. Any serious adverse events and/or serious problems will be reported to the IRB within 5 business days

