7.0 Privacy and Confidentiality

The proposed work requires the collection of protected health information.

All study personnel who will have access to protected health information and/or will be involved in obtaining subject consent will be required to complete all necessary training in the protection of human subjects and privacy through the Department of Veterans Affairs (VA) Learning University Talent Management System (TMS) and Collaborative Institutional Training Initiative (CITI) Program.

To safeguard against potential loss of confidentiality, all subjects will be given a unique study ID, and data collected for this study will be associated with study IDs only. A separate crosswalk file linking study IDs with personal identifiers will be kept in separate from data analysis files. Data analysis files will not contain personal identifiers. Data analysis will be conducted using only the de-identified data files.

Veteran, caregiver, and clinician interview and survey responses will also be kept confidential and not shared with each other or anyone outside the study team. Study data will be aggregated for presentations or publications related to the study in order to conceal the identities of subjects.

The Head of the Division of Nephrology will be notified of any adverse events or changes to the study protocol.

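### Section 6.0 conflicts with the risk named in 5.9, and 5.7 plans no by-arm summary of deaths or serious adverse events to set beside utilization

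*Combined protocol and SAP*

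**What the plan says.** **Expectation.** Section 6.0 states: "The investigators do not anticipate any adverse events that might occur".

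**Named risk.** Section 5.9 lists discontinuity of care as an anticipated risk for Veterans randomized to the Program, who change primary and, where applicable, nephrology providers. Of that change it says: "This can lead to delays in addressing health problems". The mitigation includes a "first visit with the Program clinicians within 3-months of enrollment in the Program".

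**Handling of events.** Section 6.0 provides that "any and all unanticipated problems, serious adverse events and protocol deviations will be recorded and reported immediately to the study Principal Investigator", and adds: "Any serious adverse events and/or serious problems will be reported to the IRB within 5 business days". Section 7.0 adds: "The Head of the Division of Nephrology will be notified of any adverse events or changes to the study protocol". None of these passages defines a serious adverse event or says how, or how often, events are to be looked for.

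**Follow-up and data.** Section 5.6 states: "Subjects will be followed through death, study withdrawal, or 1-year follow-up, whichever comes first". It gives comparison of the two arms as the purpose of its measures, and it has hospital, nursing-facility and emergency use abstracted from the medical record, with no difference by arm.

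**Analysis.** Section 5.7 describes enrollment, attrition and reasons for withdrawal. Its exploratory list opens with healthcare utilization and closes with "quality of life, and treatment with dialysis during follow-up using proportions and means where appropriate". Deaths, serious adverse events and time to the first Program visit are not in either list.

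**The concern.** There are three linked problems.

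1. Sections 5.9 and 6.0 do not agree. One names a way in which the intervention could harm patients; the other says nothing of the kind is foreseen. Section 2.0 describes the illness as life-limiting, with frequent hospitalization, so deaths and admissions will occur whatever their cause.

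2. Follow-up is cut short by death and withdrawal, yet the planned utilization summaries have no denominator of time at risk and no deaths beside them. A Veteran who dies in month 2 contributes few admissions. In a table of means this looks like low use of care. Hospital and emergency use is among the preliminary outcomes that a later trial would draw on.

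3. Section 6.0 gives no search method for serious events. Section 5.5 has Program teams meet monthly to review admissions and emergency visits, and describes nothing parallel for usual care. Serious events that reach the investigators by passive report may therefore surface more readily in the Program arm. Single-case reports to the IRB do not show the balance between arms.

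**Working it through.** The documents give no event rate, power calculation or safety figure, so there is no stated figure to reproduce. The check is a comparison of the text followed by three illustrations.

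**Text**

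| Item | Collected? | Summary planned in 5.7? |
|---|---|---|
| Hospital, emergency, nursing-facility use | Yes, all Veterans, record review (5.6) | Yes, descriptive; neither by arm nor person-time is stated |
| Death | Ends follow-up (5.6) | Not named |
| Serious adverse events | Recorded and reported (6.0); no search method | Not named |
| Time to first Program visit | Retrievable, since Program contacts are charted (5.5) | Not named |

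**Inputs.** 30 Veterans (Abstract) with 1:1 allocation (5.5) gives about 15 per arm. Follow-up is at most 1 year (5.6). All event rates below are assumptions.

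**1. Are deaths foreseeable?** Assume 1-year mortality of 10% to 30%.
- Expected deaths: 30 × 0.10 = 3, to 30 × 0.30 = 9.
- Chance of no death: 0.9^30 = 0.042 at 10%; 0.8^30 = 0.0012 at 20%.

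**2. How far can a mean per Veteran mislead?** Suppose both arms use care at the same constant rate r per year alive. Let a fraction d of an arm die, on average at time t (in years), with no withdrawals. Expected events per Veteran = r × [1 − d(1 − t)]. The rate r cancels in the ratio of arms. Taking the two ends of the assumed range as the two arms, d = 0.30 against d = 0.10:

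| Mean time of death t | 1 − 0.30(1 − t) | 1 − 0.10(1 − t) | Ratio | Apparent reduction |
|---|---|---|---|---|
| 0 (limit) | 0.700 | 0.900 | 0.778 | 22% |
| 0.25 | 0.775 | 0.925 | 0.838 | 16% |
| 0.50 | 0.850 | 0.950 | 0.895 | 11% |
| 1 (limit) | 1.000 | 1.000 | 1.000 | 0% |

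At t = 0.50 the arms have 15 × 0.85 = 12.75 and 15 × 0.95 = 14.25 person-years. Dividing events by person-years returns r in both arms and removes the artefact. Withdrawal acts in the same way. If use rises shortly before death, the distortion can shrink or reverse. For that reason deaths must be shown beside the rates as well.

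**3. What could a by-arm table show with 15 per arm?**
- Chance of at least one event in an arm, 1 − (1 − p)^15: 54%, 79%, 96.5% and 99.5% for p = 5%, 10%, 20% and 30%.
- Exact two-sided 95% upper limit after 0 of 15: 1 − 0.025^(1/15) = 21.8%.
- 95% half-width for a difference, 1.96 × √[2p(1 − p)/15]: 0.215, 0.286, 0.328 and 0.358 for common p = 10%, 20%, 30% and 50%.
- Power at two-sided 0.05: 22% for 20% against 40%, and 37% for 30% against 60%.

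Events would be seen, but differences between arms would be poorly estimated. A description is feasible; a formal test would be uninformative.

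**The case against.** A reader might infer that harms are never compared between arms. The documents do not support that. Section 5.6 has a stated comparative purpose and collects hospital, emergency and nursing-facility use, dialysis and quality of life in both arms; section 5.7 describes them; section 6.0 records serious events. Nor does the gap follow from the sentence in 6.0. It comes from what 5.7 leaves out.

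A reader might also infer that admissions will be counted more fully in the Program arm. That is not supported either. The record review covers every Veteran's chart, including scanned outside records, and the monthly team meetings are clinical care, not the study's stated means of counting admissions. Uneven detection remains a concern only for serious events passively reported under 6.0.

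Section 6.0 can be read as saying that no adverse events are expected to result from taking part. Deaths are plainly foreseen elsewhere, since follow-up runs to death and the Program includes end-of-life care. On that reading the chance of zero deaths refutes nothing, and a possible delay in care is a risk rather than an event. This is fair, and it softens the conflict. It does not remove it: delayed attention to health problems is a risk of taking part, and 6.0 neither refers to it nor says which events are expected from the illness itself.

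Finally, this is a feasibility pilot that claims no safety conclusion, and a table from about 15 per arm would not support one. That stands. It limits what the table can be used for; it is not a reason to omit deaths.

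**Conclusion.** The point holds in a limited form. Section 6.0 needs reconciling with 5.9, and 5.7 should show deaths and serious adverse events by arm beside utilization. The textual findings rest on no assumption. The size of the utilization artefact does: 0% to 22%, about 11% with deaths at mid-year, for 30% against 10% mortality, equal constant use while alive and no withdrawals. The documents give no mortality figure, and nothing in them suggests that mortality will differ between arms; the illustration shows what the planned summary could hide, not what is expected.

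The stronger claims, that harms go uncompared or that a corrected plan could establish safety, are not supported. This is an inexpensive improvement to reporting, not a flaw in the trial's primary aim.

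**What to change.** 1. **Section 6.0.** Replace the opening sentence with one that agrees with 5.9 and names death, hospitalization and emergency visits as events expected in this population. Define a serious adverse event. Leave immediate reporting unchanged.
2. **Ascertainment.** State that deaths and serious adverse events are identified in both arms by the same quarterly study visits and the same record review.
3. **Section 5.7.** Add a descriptive table by randomized arm giving deaths, serious adverse events, and hospital, emergency and nursing-facility use, with person-time and confidence intervals. State that there is no formal test and that no safety conclusion will be drawn.
4. **Time to first Program visit.** Report this from randomization, for the Program arm only, as a feasibility measure. It has no counterpart under usual care and cannot be compared between arms.

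The cost is a short edit to 6.0 and a small amount of tabulation, largely from data already recorded. Sample size, treatment and visit schedule do not change. The drawback is that the estimates will be imprecise, which the intervals will make plain.
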